# 3.3 Recruitment Process

Study coordinators will screen records of previous study participants who have agreed to future contact and UW specialty clinics based on the aforementioned criteria in 3.1 & 3.2.

### **Previous Studies:**

• Participants enrolled in the MEND and the Seattle Kidney Study have documented consent approving contact regarding participation in future studies.

### **UW Clinics:**

Version 2.0

• Additional sources of recruitment will include the nephrology clinics in the University of Washington System (University of Washington Medical Center, and Harborview Medical Center), community based nephrology practices, and self-referrals from the Kidney Research Institute Community Connection website.

## 3.4 Co-Enrollment Guidelines

Study participants will not be allowed to enroll in other clinical trials, as the effect of Coenzyme Q10 and Nicotinamide Riboside on this population is not clear.

### 3.5 Participant Retention

Every effort to retain enrolled participants will be made throughout the duration of the study in order to reduce bias related to loss to follow-up. Strategies for participant retention include:

- Thorough explanation of the importance of all 3 study treatment groups to the overall success of the study
- Detailed explanation of the study visit schedule and procedural requirements during the informed consent process, with re-emphasis at the end of each study visit
- Use of appropriate and timely visit reminder mechanisms. This includes midtreatment phone call to assess participant adherence to regimen and remind participants of subsequent follow up visits
- Compensating participants for their time and effort in the study
- Immediate and multifaceted follow-up on missed visits

# 3.6 Participant Withdrawal

Participants will be allowed to voluntarily withdraw from the study for any reason and at any time. The investigator may withdraw participants from the study in order to protect their safety or if they are unwilling or unable to comply with required study procedures after consultation with the study sponsors and co-sponsors. Participants also may be withdrawn if the study sponsor, government or regulatory authorities, or site IRBs/ECs terminate the study before the planned end date. Reasons for withdrawal from the study will be recorded and a final evaluation will be made if feasible.

Participants who discontinue treatment but remain in the study will continue to be followed-up whenever possible.

# 4.0 STUDY TREATMENT/PRODUCT/INTERVENTION

### 4.1 Treatment/Product/Intervention Regimen(s):

Participants will be randomized to in treatment order to receive the following medications for 6 weeks plus an additional 1 week in case of logistical difficulties with scheduling study visits.

- Nicotinamide Riboside (Tru Niagen by Chromodex) at 1000mg/day in the form of two 250mg tablets twice daily.
- Coenzyme Q10 will be administered at 600mg twice daily.
- **Placebo** will consist of identical appearing pill. This will be a double dummy with 4 tablets appearing identical to NR and 2 tablets appearing identical to CoQ10.

Randomized Tx Order 1 st , 2 nd , 3 rd	Total Dosage QD	Regimen	Duration
Nicotinamide Riboside	1000 mg	250 mg tabs x2 BID	6 weeks (+/- 7 days)
Coenzyme Q10	1200 mg	600 mg tabs BID	6 weeks (+/- 7 days)
Placebo	N/A	BID	6 weeks (+/- 7 days)

# 4.2 Treatment/Product/Intervention Supply and Accountability

The University of Washington Investigational Drug Services (IDS) will manage the study drugs. IDS will manage treatment randomization. Study coordinators will alert IDS before a scheduled baseline and subsequent visits and pick up the study drugs for administration.

The IDS pharmacist must maintain complete records of all study drugs/products received from the Clinical Research Products Management Center and drug manufacturer and subsequently dispensed to study participants. All unused supplies must be returned to the Clinical Research Products Management Center after the study is completed or terminated.

# 4.3 Adherence Assessment

Adherence to the study treatment will be assessed by study coordinator phone call midway through each treatment arm to assess adherence and inventory method to assess remaining medication/placebo at the end of the study. Adherence will be defined as consumption of at least 75% of the prescribed regimen. Up to 36 participants may be recruited to compensate for non-adherence or drop-out with the goal of 10 individuals completing in each treatment arm. Participants will be asked to bring in unused study drugs at each visit to return to IDS.

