#### **SCHEMA**

Purpose:	Study the impact of oral nicotinamide riboside vs CoQ10 on aerobic capacity, muscle performance and mitochondrial metabolism among persons with moderate-severe CKD.
Design:	Randomized, placebo controlled cross-over trial
Study Population:	Adults age 30-79 with moderate-severe CKD eGFR by CKD (EPI equation) $< 50 ml/min/1.73 m^2$
Study Size:	30 (10 in each of 3 arms).
Treatment Regimen:	
 
Nicotinamide riboside 1000mg daily (250mg - 2 tablets twice daily)
 
Coenzyme Q10 1200mg daily (600mg - 1 tablets twice daily)
 
Placebo (sugar pill)
 

Study Duration:	1.5-2 year

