## 4.4 Toxicity Management

Currently, the mechanism whereby Coenzyme Q10 and Nicotinamide Riboside may cause harm or toxicity is unknown. There have been studies demonstrating slightly decreasing hemoglobin and potassium in healthy controls treated with NR^13. In the event of moderate or serious adverse effects (as defined in section 6.2) requiring treatment for such conditions as nausea, vomiting, or abdominal pain thought to be related to toxicity from the study drug, the patient will be withdrawn from the study and adverse events reported.

Mild adverse events that do not requiring treatment and are thought to be potentially related to toxicity from the drug will prompt a 50% dose reduction.

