### 7.3 Accrual, Follow-up, and Sample Size

The overall sample size for this project is 30. We anticipate recruiting 1-2 participants weekly for total study duration of 1.5-2 years (Table 2).

Order	Ν	Period 1	Period 2	Period 3
Sequence Placebo-CoQ10-NR (n=5)	10	A	В	C
Sequence Placebo-NR-CoQ10 (n=5)		A	C	В
Sequence NR-Placebo-CoQ10 (n=5)	10	В	A	С
Sequence NR-CoQ10-Placebo (n=5)		В	C	А
Sequence CoQ10-Placebo-NR (n=5)	10	С	A	В
Sequence CoQ10-NR-Placebo (n=5)		С	В	А

Table 2. Study design and sample size. Given the efficient cross-over design, 30 participants will receive each treatment by the end of the study.

Sample size was calculated based on values obtained from an standard deviation of the difference of VO2max on bicycle ergometry from a prior study of 2.1ml/kg/min. A total of 30 patients will enter this three-treatment crossover study. A total of 30 patients will enter this two-treatment crossover study. The probability is 80 percent that the study will detect a treatment difference at a two-sided 0.05 significance level, if the true difference between treatments is 2.1 (1 SD)ml/kg/min. This is based on the assumption that the standard deviation of the difference in the response variables is 2.1 ml/kg/min (Table 3). Sample size was calculated using the following sample size calculator: *http://hedwig.mgh.harvard.edu/sample\_size/js/js\_crossover\_quant.html* 

	VO2max Power	
Minimal detectable difference	80% (n)	90% (n)
0.5 SD	34	44
0.75 SD	16	21
1 SD	10	13

Table 3. Total samples size required to detect treatment effects for aerobic capacity bicycle ergometry from crossover design. Based on published study demonstrating the effect of a 12mo combined resistance and aerobic exercise program resulting in an increase of +5.7 ml/kg/min VO2peak with a standard deviation of the difference of 2. 1 ml/kg/min.

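### Recruitment is set by a completer goal that counts non-adherence as a loss, and no analysis set is defined, so a completers' comparison is permitted though not stated

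*Combined protocol and SAP*

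**What the plan says.** All references are to the combined protocol and SAP.

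- **Section 4.3** sets the recruitment ceiling and its purpose: "Up to 36 participants may be recruited to compensate for non-adherence or drop-out with the goal of 10 individuals completing in each treatment arm". It also sets the threshold: "Adherence will be defined as consumption of at least 75% of the prescribed regimen".
- **Schema and section 7.3** size the trial at 30. The Schema has "30 (10 in each of 3 arms"), and section 7.3 has "A total of 30 patients will enter this three-treatment crossover study". The note to Table 2 adds that "30 participants will receive each treatment by the end of the study". Since everyone is meant to receive all three treatments, ten per arm can only mean the three groups defined by first treatment, each a pair of sequences in Table 2.
- **Section 4.4** withdraws from the study participants with moderate or serious effects that need treatment and are attributed to study drug. For mild effects, those "thought to be potentially related to toxicity from the drug will prompt a 50% dose reduction".
- **Section 7.6.1** names an ANOVA with sequence, treatment and period effects. It gives no analysis population, no rule for a missing period and no rule for participants below 75%. The random-intercept mixed model under Secondary Analyses is for metabolites only.
- **Sections 3.5, 3.6 and 4.5** point towards keeping data. They commit to retention, to follow-up where possible after treatment is stopped, and to continued procedures (except MRS) after a pregnancy.

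**The concern.** The goal is counted in completers, and non-adherence is listed separately from drop-out. A participant who takes too little study product can still attend every visit and have VO2max measured. Recruiting someone else to make up for that person suggests that the first may not count towards the 30. With no analysis set in section 7.6.1, the choice between all randomised participants and adherent completers could be made after the data are seen.

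Both kinds of loss arise after randomisation, and section 4.4 ties some of them to the study drug. If participants who tolerate a drug poorly also respond differently to it, averaging the within-participant contrast over completers alone estimates the effect in a selected group. Outcomes already measured in the other participants would also be set aside.

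**Working it through.** **1. Reproduce the plan's sample size.** Inputs from section 7.3: SD of the within-participant difference 2.1 ml/kg/min, two-sided 0.05. For a paired t-test, power comes from the noncentral t with n − 1 degrees of freedom and noncentrality d√n, where d is the difference in SD units. The smallest n for 80% and 90% power is 10 and 13 at 1 SD, 16 and 21 at 0.75 SD, and 34 and 44 at 0.5 SD. All six cells of Table 3 match.

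**2. What the extra six represent.** Section 4.3 gives no expected loss rate. The implied allowance is 1 − 30/36 = 16.7%, or six per sequence where Table 2 has five.

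**3. Are they needed for the stated power?** Section 7.3 claims 80% power at an assumed effect of 1 SD, that is, 2.1 ml/kg/min. At that effect, power is 80.3% with 10 participants and 99.96% with 30. The stated target therefore does not depend on having 30 completers. Numbers matter for smaller effects: the difference detectable with 80% power is 0.60 SD (1.25 ml/kg/min) with 24, 0.53 SD (1.11) with 30 and 0.48 SD (1.01) with 36.

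**4. Possible bias of a completers' mean.** Suppose 30 completers have mean effect 2.1 and the six others have mean effect e. The documents give no value for e. The mean over all 36 is (30 × 2.1 + 6e)/36, and the completers' mean exceeds it by (6/36)(2.1 − e).

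| Assumed e (ml/kg/min) | Mean over 36 | Excess of completers' mean |
|---|---|---|
| 2.1 | 2.10 | 0 |
| 0 | 1.75 | 0.35 (2.1/1.75 = 1.20) |
| −1 | 1.58 | 0.52 |
| −2.1 | 1.40 | 0.70 |

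For scale, the standard error with 30 is 2.1/√30 = 0.38. If e were above 2.1, the completers' mean would be too low.

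**5. Dose reduction and the 75% threshold.** If a fraction f of a period is spent on half dose, consumption relative to the full regimen is 1 − 0.5f. This is below 0.75 only when f > 0.5; a reduction at mid-period gives exactly 75%. If the reduced dose is itself the prescribed regimen, a reduction need not lower adherence at all. Section 4.3 does not say which denominator applies.

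**6. Power if everyone is analysed.** Assume that six of 36 have zero effect, so the mean effect is 5/6 of that in the others, that the SD of the difference stays at 2.1, and that all 36 contribute a contrast.

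| Effect in responders | All 36, six at zero | 30 completers |
|---|---|---|
| 1 SD | 99.8% | 99.96% |
| 0.75 SD | 95.4% | 97.8% |
| 0.5 SD | 68.1% | 75.4% |

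**7. Do incomplete sequences carry information?** Take Table 2's 30 participants, with one per sequence missing period 3, and fit participant, period and treatment effects. The standard error of a treatment contrast is 0.272 times the residual SD if the six are kept and 0.289 times if they are dropped.

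**The case against.** The strongest reply is that over-recruitment is not exclusion. Section 4.3 sets a ceiling and a goal. It does not say that anyone is removed from analysis, nor that recruitment continues until ten per group have completed. Raising the number to allow for non-adherence is also ordinary practice when everyone is analysed, because non-adherence dilutes the effect: with 0.5 SD in five sixths and zero in the rest, analysing everyone gives 59.7% power at 30 and 68.1% at 36. Sections 3.5, 3.6 and 4.5 favour keeping data. This stands, and it rules out saying that the plan excludes these participants. It does not supply the missing rule: the follow-up provisions produce off-treatment outcomes without saying whether they are used, and section 4.4 removes the drug-related cases from the study altogether.

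Three further inferences are tempting, and the documents do not support them.

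- *The ANOVA drops incomplete participants.* Section 7.6.1 states no complete-case rule, and step 7 shows that an ANOVA with participant effects uses those with two periods. It depends on how the model is fitted.
- *Anyone on a reduced dose must fall below 75%.* Step 5 shows that this depends on timing and denominator.
- *A completers' analysis would overstate the benefit.* Nothing in the documents links tolerability to VO2max response, and non-adherence can also occur on placebo. The direction is plausible but not established.

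**Conclusion.** The concern holds as an omission that leaves room for bias. Section 4.3 defines success by completers and treats low consumption as a loss to be made up, the trial is sized for 30, and section 7.6.1 names no analysis set. A completers' comparison is therefore permitted and suggested, but not specified. A reader might infer that one has been adopted as a rule; no section says so.

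Up to six of 36 participants (17%) are involved. The 20% excess is an illustration, not an estimate. It requires all six to be left out and to have zero effect while the other 30 have 2.1. It also treats the six as having a defined effect, although some withdrawn under section 4.4 will have no later VO2max. What the documents do establish is that loss can depend on treatment and that nothing fixes in advance whose data count.

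**What to change.** In sections 4.3 and 7.6.1:

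- Make the primary analysis set all randomised participants (up to 36), analysed by the treatment assigned in each period, using every available period VO2max regardless of adherence.
- Fit a mixed model with sequence, period and treatment effects that accepts incomplete sequences.
- Describe the extra six as over-enrolment to offset lost precision, not as replacements, and state how they are allocated to the six sequences.
- Use the 75% adherence set for a supportive analysis only.
- Reconcile sections 4.3 and 4.4 on whether adherence is judged against the original or the reduced dose.

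The cost is wording. The estimate may be somewhat smaller than a completers' estimate, with the power shown in step 6. Outcomes never measured after withdrawal are not recovered: the model relies on the loss being explained by the observed data, and a participant lost during the first period adds little or nothing to a within-participant contrast. Reasons and timing of withdrawal should therefore be reported by treatment.

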## 4.4 Toxicity Management

Currently, the mechanism whereby Coenzyme Q10 and Nicotinamide Riboside may cause harm or toxicity is unknown. There have been studies demonstrating slightly decreasing hemoglobin and potassium in healthy controls treated with NR^13. In the event of moderate or serious adverse effects (as defined in section 6.2) requiring treatment for such conditions as nausea, vomiting, or abdominal pain thought to be related to toxicity from the study drug, the patient will be withdrawn from the study and adverse events reported.

Mild adverse events that do not requiring treatment and are thought to be potentially related to toxicity from the drug will prompt a 50% dose reduction.

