# 3.2 Exclusion Criteria

- Pregnant
- On chronic dialysis
- Expectation to start dialysis within 6 months
- Insulin dependent diabetes
- Severe anemia: hemoglobin <8gm/dL
- Hyperkalemia: K>5.7
- Kidney transplantation
- Weight >300 lbs
- HIV
- End stage liver disease with cirrhosis
- Oxygen-dependent COPD
- Unable to walk unassisted from room to room in own house
- Institutionalization, or inability to consent
- Use of immunosuppressive medications (i.e. steroids, calcineurin inhibitors)
- Malignancy requiring active treatment or currently under surveillance at the discretion of the investigator
- Pacemaker
- Current participation in another interventional trial
- Non-English speaking
- Hospitalization for heart attack, stroke, or unstable cardiac chest pain in last 3 months (e.g. myocardial infarction, unstable angina, cerebrovascular accident)
- Any severe medical condition that the investigator feels would disqualify a patient from aggressive exercise.
- Baseline systolic blood pressure >170 or diastolic blood pressure >100
- Persistent or permanent uncontrolled arrhythmia at the discretion of the investigator.

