### Screening visit/practice bicycle visit

The screening visit will take place within 28days of the baseline visit. Some components of the initial screening visit may be performed by telephone or in combination with other study visits in order to best accommodate participants' schedules. The screening visit will occur at the prevention center. Study coordinators will obtain informed consent prior to any data acquisition or sample collection

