### Screening visit procedures:

- Verification of inclusion and exclusion criteria as outline in sections 3.1 & 3.2 including
- Vital signs and anthropometrics
- 6-minute walk: Participants able to walk 500 meters or more during 6 minutes will be excluded from the study
- *Screening labs (if 6 minute walk <500meters or less):* A renal panel & Complete blood count (CBC)
- Bicycle ergometry practice: The exercise trainer will help familiarize the participant with the bicycle to mitigate significant training effects due to lack of exposure to the equipment
- Questionnaires will be handed out to be returned at the baseline visit. Participants may also choose to complete these at the baseline or online via RedCap ITHS
  - Medical History Questionnaire
  - o Kansas City Cardiomyopathy Questionnaire

Eligibility for the study will be at the discretion of the principal investigator or study clinician after review of the pertinent labs and inclusion/exclusion criteria.

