# Baseline visit and Post-treatment visits (2, 3, 4)

The participant will have been required to fast for at least 6 hrs prior to each visit and abstain from caffeine or smoking before bicycle ergometry testing. Patient should avoid exercise 48hours prior to cycle ergometry. Treatment will be dispensed after cycle

ergometry at baseline and post-treatment visits 2,3 and 4. The following data will be obtained:

- Vital signs.
- Fasting blood collection for banked plasma and peripheral blood mitochondrial energetics.
- Anthropometrics (height and weight and waist to hip ratio)
- Urine pregnancy test will be given to women of child-bearing potential
- Resting energy expenditure (REE) and cycle ergometry will be performed at the Prevention center.
- The optional MRS and Muscle Fatigue tests will occur at the diagnostic imaging center at UWMC at baseline and in the same week of visits 2, 3 and 4 while patient remains on study drug. Patient should wait avoid heavy exercise for 48hrs before MRS.
- Questionnaires will be administered (PROMIS fatigue short form 17, PROMIS physical function short form 20a, and Kansas city heart failure questionnaire)

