# Blood Collection:

- NAD samples will be obtained from fasting whole blood collected in one 2.7ml Blue (sodium citrate tube). From the blue tube, after inversion mixing, 0.5ml will be pipetted into 2 cryotubes **on dry ice.** Samples will be immediately frozen on dry ice and placed in -80C ASAP. Samples will be sent to [name] in clinical pharmacology ([contact]).
- EDTA Plasma samples will be sent to University of California at Davis West Coast Metabolomics for liquid chromatography high-resolution mass spectrometry (LC-MS) for targeted metabolomics analysis. We will perform additional transcriptomics using mRNA samples obtained from Paxgene tubes which will also be sent to West Coast Metabolomics.
- Paxgene mRNA will be obtained at baseline and post-intervention visits.
- Clinical laboratory assays for determination of comprehensive metabolic panel (electrolytes, blood urea nitrogen, creatinine, glucose, albumin, total protein, calcium, alkaline phosphatase, ALT, AST, total bilirubin), CPK, lactate, triglyceride will be performed at the *KRI Core Research laboratory*.

*Urine collection:* **Spot urine** for metabolomics will be collected at baseline and after each treatment period (visits 2-4).

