## 9.2 Reference Laboratory Specimens

- Blood for metabolomics testing. Aliquots of EDTA preserved blood will be stored at -80°C. All samples will be de-identified.
- Blood for F2-isofuran and F2-isoprostane assays will be frozen at -80°C and sent in bulk to Vanderbilt University (c/o [name]).
- EDTA plasma samples and urine samples used for metabolomics and Paxgene samples for transcriptomics will be sent at the conclusion of the study to [name] at UC Davis for analysis by West Coast Metabolomics: ([contact])

Tube	Size	Number of	Aliquots for banking	Purpose
		tubes		
Blood Screening only:	-			
CBC (lavender)	3ml	1	none	Send to Qwest labs for
Renal panel (green)	4ml	1		hemoglobin and renal panel
Blood banking at basel	ine and after	each treatment		
EDTA whole blood	10ml	3	none	Fresh for [name] lab
(lavender)				
EDTA plasma	8ml	2	0.5ml x 10	Metabolomics
(lavender)			1ml x 3	Lipids
				F2 isoprostanes/isofurans for
				Vanderbilt.
Serum (red)	6ml	1	0.5mlx6	biochemistry
ACD (citrated plasma)	2.5ml	1	0.5ml x2 on dry ice	For NAD. Aliquot immediately
whole blood (blue top)				onto tubes chilled on dry ice
Paxgene tube	2.5ml	1	2.5x1	Banking
Urine banking at	10ml		1mlx5	Urine metabolomics
baseline and at end of				Urine urea nitrogen
each treatment				Urine creatinine
				Urine ammonia

Table 4. List of blood and urine samples to be collected during study.

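### Hemoglobin is planned only at screening, although Section 4.4 cites a slight fall with NR, so there is no scheduled on-treatment value for safety or for interpreting a null VO2max result

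*Combined protocol and SAP*

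**What the plan says.** Section 4.4 (Toxicity Management) names two laboratory changes with NR: "studies demonstrating slightly decreasing hemoglobin and potassium in healthy controls treated with NR". It gives no size for either.

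Hemoglobin appears in the plan as follows.

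- Section 3.2 excludes "Severe anemia: hemoglobin <8gm/dL", so patients at or above 8 g/dL may enter.
- Section 5.0 places a CBC among the screening laboratory tests. On timing: "The screening visit will take place within 28days of the baseline visit".
- Table 4 (Section 9.2) lists the CBC tube under "Blood Screening only". The block for baseline and after each treatment has no CBC tube.

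For baseline and visits 2, 3 and 4, Section 5.0 lists "Fasting blood collection for banked plasma and peripheral blood mitochondrial energetics". Its Blood Collection part adds a "comprehensive metabolic panel (electrolytes, blood urea nitrogen, creatinine, glucose, albumin, total protein, calcium, alkaline phosphatase, ALT, AST, total bilirubin), CPK, lactate, triglyceride". That list covers potassium but contains no hemoglobin or CBC. Section 9.1 gives local laboratory work as chemistries and pregnancy testing. Table 1 marks screening labs in the screening column only. It has a general blood row at later visits, whose contents are those itemized in Section 5.0 and Table 4.

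**The concern.** The protocol cites two laboratory changes with NR and schedules follow-up of one. Two things are at stake.

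**Safety.** Section 6.2.1 finds adverse events initially by interview, and a modest fall in hemoglobin may cause no complaint. The tolerability reports on the first five subjects (Section 6.1) would contain no planned data on it. The population has moderate to severe CKD, and the entry limit admits patients who are already anemic.

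**Interpretation.** VO2max is the main outcome, and hemoglobin carries the oxygen that VO2max measures. The hypothesis in Section 1.3 is mitochondrial. If NR shows no gain in VO2max, the muscle may not have responded, or a muscle response may have been offset by reduced oxygen carriage. Same-visit hemoglobin would bear directly on that question.

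**Working it through.** **Step 1: is there any hemoglobin value after screening?**

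| Place | Hemoglobin or CBC? |
|---|---|
| Section 5.0, screening procedures | Yes, once |
| Section 5.0, baseline and visits 2, 3, 4 | No |
| Section 5.0, Blood Collection | No (electrolytes present) |
| Table 1 | Screening labs at screening only; later blood row not itemized there |
| Section 9.1 | No |
| Table 4 | Screening block only |

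The stored samples do not fill the gap as planned. Plasma and serum cannot give hemoglobin, the frozen whole-blood aliquots are assigned to NAD, and the fresh EDTA whole blood goes to cell bioenergetics.

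**Step 2: reproduce the plan's sample-size figures.** Section 7.3 uses a standard deviation of the within-patient difference of 2.1 ml/kg/min and a two-sided 0.05 level. For a paired t-test with n patients, power is the probability that a noncentral t variable with n − 1 degrees of freedom and noncentrality (difference / 2.1) × √n exceeds the critical value in absolute size. The smallest n reaching 80% / 90% power is 34/44 at 0.5 SD, 16/21 at 0.75 SD and 10/13 at 1 SD. All six cells of Table 3 are reproduced exactly.

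At n = 30 the same formula gives 80% power for 0.529 SD, that is 0.529 × 2.1 = 1.11 ml/kg/min. It gives 99.96% power for the 2.1 ml/kg/min difference named in the text.

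**Step 3: how much could a fall matter?** The documents give no fall, no starting VO2max and no mean hemoglobin. The following are assumptions, not trial figures: VO2max falls in proportion to hemoglobin with no compensation, starting VO2max is 15 to 25 ml/kg/min, and mean hemoglobin is 10 to 14 g/dL.

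Loss = VO2max × fall / hemoglobin. For a 0.25 g/dL fall the range runs from 15 × 0.25 / 14 = 0.27 to 25 × 0.25 / 10 = 0.625 ml/kg/min. Net effect = muscle benefit − loss, entered in the power formula at n = 30.

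| Assumed fall (g/dL) | Loss (ml/kg/min) | Power, muscle benefit 2.1 | Power, muscle benefit 1.11 |
|---|---|---|---|
| 0 | 0 | 99.96% | 80% |
| 0.25 | 0.27 to 0.625 | 96.1% to 99.6% | 23.1% to 56.5% |
| 0.5 | 0.54 to 1.25 | 57.3% to 97.6% | 5.0% to 30.5% |
| 1.0 | 1.07 to 2.50 | 5.0% to 73.7% | about 5% |

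Where the assumed loss equals or exceeds the benefit, the net effect was set to zero, so power equals the 5% level. These are powers to detect NR's net effect. They do not measure bias: with a fall, the net effect really is smaller.

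**Step 4: cost in blood.** One 3 mL tube at four draws is 4 × 3 = 12 mL. Against the stated 245 mL that is 12 / 245 = 4.9%, for a total of about 257 mL. The sample size does not change.

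**The case against.** A reader might infer that an unmeasured hemoglobin fall would mask or distort the VO2max result. The documents do not support that. The primary objective is whether supplementation improves aerobic capacity compared with placebo. A fall caused by NR is on the pathway from treatment to outcome and is part of NR's total effect. If it cancels a muscle benefit, concluding that NR does not improve aerobic capacity is correct. Bias would need a further step, such as hemoglobin still depressed after the one-week washout. Section 7.6.1 allows for residual effects up to three weeks, but nothing in the documents says hemoglobin behaves that way. This objection stands in full.

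The trial also has other mechanistic evidence: monocyte reserve capacity, metabolomics and work efficiency, plus optional MRS in a subset of 20. Better mitochondrial readouts with flat VO2max would hint at an offset. This stands in part, because none of these measures shows whether hemoglobin actually fell.

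The signal itself is modest. Section 4.4 calls the change slight and places it in healthy volunteers. Its reference is titled as an open-label, non-randomized pharmacokinetic study, which Section 8.2 also cites for safety. The largest losses in the table need falls that are hard to call slight. This stands, and it limits what can be said about size.

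A reader might also infer that a fall would go wholly undetected. That is too strong: Section 6.2.1 provides for interviews, participant calls and outside medical records, so symptomatic anemia could surface. Some screening components may be combined with other visits, so a screening CBC might occasionally coincide with baseline. Neither route gives a scheduled on-treatment value.

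Finally, adjusting VO2max for same-visit hemoglobin conditions on a post-treatment variable and would not cleanly separate the two explanations. This stands and shapes the fix.

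**Conclusion.** The schedule gap is certain on the text: potassium is followed on treatment, and hemoglobin, named in the same sentence, is not. The consequences are the absence of planned safety data on a cited effect and a weaker basis for explaining a null or reduced NR result on VO2max. The validity of the randomized comparison is not in question.

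The effect on VO2max cannot be sized from the documents. Under the stated assumptions, a 0.25 g/dL fall hardly matters if the muscle benefit is the planned 2.1 ml/kg/min (power at least 96%). It matters considerably if the benefit is near the 1.11 ml/kg/min that 30 patients can detect with 80% power (23% to 57%). Those figures show only that the question is worth a routine assay, not that a material loss is expected. The change is worth making because it is cheap.

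**What to change.** Add a CBC, or hemoglobin alone, to the fasting draws at baseline and visits 2, 3 and 4, and enter it in Section 5.0, Table 1 and Table 4. Update the blood volume in Section 9.1. In Section 7, name the NR-placebo and CoQ10-placebo differences in hemoglobin as safety outcomes, each with a confidence interval.

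Keep the unadjusted VO2max comparison as primary. Label any analysis using same-visit hemoglobin exploratory, and state that hemoglobin is measured after treatment starts.

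The cost is one routine assay at four existing draws, a small laboratory fee and about 12 mL of blood. No visit is added. Handling needs arranging, because Table 4 sends the screening CBC to an outside laboratory and the EDTA tubes already drawn have assigned uses. Results could hint at the NR period, or bear on the dose-reduction wording in Section 4.4 and the unblinding wording in Section 7.5. Sending them to someone outside outcome assessment limits the risk to blinding. How results are acted on is for the investigators to set.
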